MCHC	Mean Cell Hemoglobin Concentration
MCV	Mean Cell Volume
NSAID	Non-Steroidal Anti-Inflammatory Drugs
PD	Pharmacodynamic
QD	Once Daily
RAASi	Renin-Angiotensin Aldosterone System Inhibitors
RBC	Red Blood Cell Count
S	Screening
SAE	Serious Adverse Event
SAP	Statistical Analysis Plan
SD	Standard Deviation
SMC	Safety Monitoring Committee
SmPC	Summary of Product Characteristics
TID	Three Times Daily
US	United States
W	Week
WBC	White Blood Cell Count

1 INTRODUCTION

Patiomer for Oral Suspension (patiomer) is a nonabsorbed, cation-exchange polymer that has been developed for the treatment of hyperkalemia. Patiomer binds potassium (K^+) predominantly in the lumen of the colon and increases fecal potassium excretion, leading to removal of potassium from the body and lowering of serum potassium levels. The drug substance consists of the polymer anion (the active moiety, patiomer) and a calcium-sorbitol counterion complex.

Patiomer (Veltassa[®]) is approved by the FDA and EMA for the treatment of hyperkalemia in adults (Veltassa PI, 2016, Veltassa SmPC, 2017).

1.1 Background

Serum potassium concentration is carefully regulated within a normal range of 3.8 – 5.0 mEq/L in adults (Rodriguez-Soriano, 1995) and approximately 90% of potassium is excreted by the kidney and 10% is excreted by the colon (Schaefer, 2005). Hyperkalemia is commonly defined as a serum potassium level above the upper limit of normal (i.e., > 5.0 mEq/L in both adults and pediatric patients). The physiologic effects of hyperkalemia can cause muscle weakness, paralysis and life threatening effects on cardiac conduction (e.g., QRS widening), arrhythmias, such as ventricular fibrillation, and sudden death (Ahmed, 2001). The deleterious effects of elevated potassium have been observed at levels as low as 5.0 mEq/L (Jain, 2012, Miao, 2011).

As in adults, children most at risk for hyperkalemia are those with CKD. In patients with CKD, the primary cause of hyperkalemia is a decrease in renal elimination of potassium, and the risk of hyperkalemia increases as renal function deteriorates (Wong, 2006). Furthermore, the use of drugs that block the renin angiotensin aldosterone system (RAAS) can increase the risk and severity of hyperkalemia in patients with underlying CKD. Given that this class of drugs has been proven to slow progression of renal disease among children with progressive CKD due to primary glomerulopathies or renal hypoplasia-dysplasia (The ESCAPE Trial Group, 2009), the management and treatment of hyperkalemia is critically important to enable the use of these agents (Wong, 2006).

Approximately 8 – 36% of adults with CKD develop hyperkalemia (Einhorn, 2009, Tzamaloukas, 1987) as defined by a serum potassium concentration > 5.0 mEq/L, which is often treated or prevented with diet, dose modifications of contributing medications, and/or dialysis (Lu, 2009). In children with CKD, the prevalence estimate of hyperkalemia has been reported in 366 patients (mean age 9.9 ± 5.1 years) at a single large pediatric nephrology center in Canada (Wong, 2006). A patient was considered to demonstrate hyperkalemia if any of the following three criteria were met: 1) any treatment with potassium binders; 2) potassium dietary restrictions; or 3) the most recent serum potassium was > 6.0 mmol/L. While the high cutoff for serum potassium as an inclusion criterion in this study may lead to an underestimation of the prevalence of hyperkalemia in CKD pediatric patients, the general tendency of increasing frequency of hyperkalemia with increasing stage of CKD is similar to the observed pattern in adults: the prevalence of hyperkalemia in children with CKD ranged from 0.9% in CKD stage 2 (GFR range 60 – 90 mL/min/1.73m²) to 5.3% in CKD stage 3 (GFR range 30 - < 60 mL/min/1.73m²) and 18.2 % in CKD stage 4 and 5 combined (GFR range 15 – < 30 mL/min/1.73m² and < 15 mL/min/1.73m²).

An analysis of the serum potassium data from the ongoing Cardiovascular Comorbidity in Children with Chronic Kidney Disease (4C) Study in Europe provides additional estimates of the frequency of hyperkalemia in the pediatric CKD population. The 4C study is a longitudinal observational study following approximately 700 children with CKD ages 6 to 17 years at the time of enrollment, and is evaluating the prevalence, clinical symptoms and progression of cardiovascular and kidney disease (Querfeld, 2010). Mild hyperkalemia defined as serum potassium of 4.8 - 5.4 mEq/L, occurred in 11.6 % of the samples analyzed in children with CKD stage 2 and increased up to 28.6 % in children with CKD stage 4 and 33.8 % in children on hemodialysis. Moderate hyperkalemia (5.5 – 5.9 mEq/L) and severe hyperkalemia (≥ 6 mEq/L), although both occurring at a lower rate, showed a similar pattern in increasing frequency with worsening kidney disease.

Hyperkalemia can occur acutely and also can be a recurring condition in patients with the above chronic conditions and drug treatments; however, the utility of current options for the management of hyperkalemia (e.g., dietary potassium restriction, diuretics, sodium bicarbonate, sodium and calcium polystyrene sulfonate) are limited and not all of them have been well studied for treatment of hyperkalemia. Some treatments for hyperkalemia such as insulin and bicarbonate, shift potassium intracellularly, but do not reduce total body potassium.

Given the limitations with current therapies and the need for a well-tolerated potassium binder to be used in both acute and chronic clinical settings, patiromer was developed as an alternative therapy for patients with hyperkalemia.

1.2 Effects in Humans

The clinical development program for patiromer to date includes eight completed studies: three Phase 1 studies, four Phase 2 studies and one two-part Phase 3 study (RLY5016-301). A total of 791 subjects participated in these eight clinical studies, including patients with hyperkalemia, CKD, heart failure, diabetes mellitus, hypertension and/or patients on hemodialysis, and healthy volunteer subjects. The 734 subjects received at least one dose of patiromer and the duration of dosing ranged from a single dose to up to 1 year.

The pivotal two-part Phase 3 study (RLY5016-301) evaluated the treatment of hyperkalemia in subjects with CKD at two starting doses, 4.2 g patiromer BID or 8.4 g patiromer BID (subjects with screening serum K^+ of > 5.0 to < 5.5 mEq/L were assigned the lower starting dose and subjects with screening serum K^+ of 5.5 to < 6.5 mEq/L were assigned the higher starting dose) (Weir, 2015). The study consisted of two parts (Part A, a 4-week treatment phase, and Part B, an 8-week, placebo-controlled, randomized withdrawal phase). In Part A, the mean (SE) change in serum potassium from baseline (mean [SD] 5.58 [0.51] mEq/L) to Week 4 was -1.01 (0.031) mEq/L (95% CI: [-1.07, -0.95]); this mean reduction in serum potassium was statistically and clinically significant. The proportion of subjects with a serum potassium level in the Part A target range of target range of 3.8 to < 5.1 mEq/L at Week 4 was 76% overall. The proportion of subjects in the target range was similar in both starting dose groups, which had been assigned according to severity of starting serum potassium level. Randomized withdrawal of the drug in the second part (Part B) confirmed the efficacy observed in Part A and provided evidence of the benefit of continued treatment with patiromer once serum potassium is controlled.

Two Phase 1 studies in healthy volunteers (RLY5016-101 and RLY5016-102) demonstrated that doses of up to 50.4 g/day patiromer were pharmacologically active (resulting in increased fecal potassium excretion in a dose-dependent manner) and well-tolerated, and that 25.2 g/day patiromer administered either QD, BID, or TID had similar pharmacological activity and tolerability. The safety, tolerability, and pharmacologic activity of QD dosing of patiromer were assessed in Study RLY5016-102. This open-label, multiple-dose crossover Phase 1 study evaluated the pharmacology, safety and tolerability of three dosing regimens of patiromer in 12 healthy subjects. Patiromer was administered orally as an aqueous suspension of 8.4 g patiromer TID for 6 days, 12.6 g patiromer BID for 6 days and 25.2 g patiromer QD for 6 days in a randomly assigned order based on one of six dosing sequences. Administration of 25.2 g/day patiromer led to a mean increase in fecal potassium excretion of approximately 1400 mg/day, with a corresponding similar decrease in urinary potassium excretion. No statistically significant difference was observed among the TID/BID/QD treatment groups with respect to the mean daily fecal or urinary potassium excretion. This was true for the overall comparison among the three treatment groups, as well as for the pairwise comparisons.

The onset of action Phase 1 study RLY5016-103 in subjects with hyperkalemia provided additional information supporting QD dosing of patiromer (Bushinsky, 2015). This was an open-label, single arm study that evaluated the time to onset of the potassium-lowering action of patiromer. Twenty-five (25) subjects with CKD (baseline mean eGFR of 34.8 mL/min/1.73m²) who had a serum potassium at Screening of 5.5 to < 6.2 mEq/L and who were not on dialysis were entered into a 3-day in-patient run-in period during which they began receiving a potassium- and sodium-controlled diet, followed by a 48-hour treatment period (fixed dose of 8.4 grams patiromer BID for a total of 4 doses, administered at Hours 0, 10, 24 and 34) during which serum potassium was assessed repeatedly. From a mean baseline serum potassium of 5.93 mEq/L, statistically significant reductions were observed at 7 hours after the first dose (0.21 mEq/L) and throughout the 48-hour treatment period ($p \leq 0.001$). After the last dose of patiromer at Hour 34, mean serum potassium values continued to decline, reaching a mean (standard deviation [SD]) maximal reduction of 0.83 (0.454) mEq/L at 7 hours after the last dose (Hour 41). By Hour 58 (i.e., 24 hours following the last dose), the mean serum potassium had returned to a level similar to that at the time of the last dose (mean [SD] serum potassium at Hour 34: 5.28 [0.373] mEq/L; at Hour 41: 5.11 [0.391] mEq/L; at Hour 58: 5.27 [0.548] mEq/L).

A comprehensive assessment of safety of patiromer for the treatment of hyperkalemia was conducted. A total number of 734 adults were exposed to at least one dose of patiromer and a pooled safety analysis was conducted in 666 subjects receiving patiromer (including 219 exposed for at least 6 months and 149 exposed for at least one year) and 49 subjects receiving placebo for up to 28 days. Data from the overall safety population demonstrated that patiromer was well tolerated. AEs and SAEs were reported in 60.8% and 8.3% of subjects, respectively, of the overall safety population receiving patiromer for up to 52 weeks. Approximately 20% of subjects receiving patiromer experienced AEs considered related to study drug but no SAEs were considered drug related. Overall, the most common reported AEs were gastrointestinal in nature and predominantly were events of constipation and diarrhea. These events tended to occur early after treatment initiation, were mild to moderate in nature, occurred in less than 10% of subjects, were self-limited and typically did not require dose reductions or discontinuations.

The most common adverse reactions (occurring in $\geq 2\%$ of subjects) in subjects treated with patiromer in the clinical trials were constipation, hypomagnesaemia, diarrhea, nausea, abdominal discomfort, and flatulence. Most adverse reactions were mild to moderate. Constipation generally resolved during the course of treatment. Refer to the current version of the Investigator's Brochure for additional information (Investigator's Brochure, 2016).

Potassium levels < 3.5 mEq/L occurred in approximately 4.7% of subjects and none of these events were serious AEs. Approximately 9% of subjects in clinical trials developed hypomagnesemia with a serum magnesium value < 1.4 mg/dL. AEs of chronic renal failure, acute renal failure and cardiac disorders events were also observed; however, these events generally were not assessed as being attributable to patiromer but consistent with AEs expected in study population with a high burden of CKD, diabetes mellitus, heart failure, and coronary artery disease.

During the clinical studies, the most commonly reported adverse reactions leading to discontinuation of patiromer were gastrointestinal adverse reactions (2.7%), including vomiting (0.8%), diarrhea (0.6%), constipation (0.5%) and flatulence (0.5%).

To date, no clinical studies with patiromer have been performed in children.

Refer to the current version of the Investigator's Brochure for a more detailed summary of these clinical studies.

1.3 Rationale

The safety and effectiveness of patiromer has not been evaluated in children. The current study RLY5016-206p is the first study to explore the use of patiromer in children and adolescents 2 – < 18 years of age.

1.4 Rationale for Study Design

Patiromer binds potassium predominantly in the lumen of the colon and increases fecal potassium excretion, leading to removal of potassium from the body and lowering of serum potassium levels. Given its mechanism of action, patiromer is expected to act similarly in adults and children and should be effective in lowering serum potassium levels in pediatric patients with hyperkalemia. Therefore, the current study focuses on patiromer dose finding in the first 14 days of the study followed by an additional 5.5-month safety follow-up.

The pediatric subjects, children and adolescents 2 – < 18 years of age, are divided into three age cohorts (2 – < 6 years, 6 – < 12 years and 12 – < 18 years). The study will commence with the oldest age cohort (12 – < 18 years) and the lowest of three patiromer starting dose levels; this is to ensure safety of younger age subjects who might be the most vulnerable to potential adverse events associated with patiromer. The SMC and DSMC will review safety and PD data from the three initial subjects. If the SMC and DSMC agree that the patiromer starting dose evaluated is appropriate, then nine additional subjects (or fewer if more than three subjects were initially enrolled) will be evaluated at this starting dose level for a total of 12 subjects at the recommended starting dose. If the SMC and DSMC do not agree that the initial patiromer starting dose evaluated is appropriate, then the next higher patiromer starting dose level will be evaluated in three additional subjects. The SMC and DSMC review process and determination of whether the

recommended starting dose was achieved or not will be repeated for these three subjects. Once the recommended patiromer starting dose is determined for a particular age cohort, no additional dose levels will be evaluated. The safety and PD data from the older age cohort will be used by the SMC and DSMC to determine the starting dose for the younger age cohorts. The total sample size could be as low as 36 (three initially treated subjects plus an additional nine if the first dose is chosen as the recommended dose for each of the three different age cohorts) or up to 54 if all three patiromer starting dose levels are studied for each age cohort.

The proposed dosing regimen in adults is once daily administration; the same dosing regimen is proposed for the pediatric population.

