--

	stopping patiromer treatment (Follow-up Visit 2). All subjects who withdraw early from treatment will enter the Follow-up Period.
DSMC Review / Starting Dose Level Assessment:	
The DSMC will determine a recommended starting dose for each age group. After three subjects at a given starting dose level provide data from the 14-Day PD / Dose Finding Phase, the DSMC will evaluate safety and PD data, including achievement of serum potassium within the target range (serum K⁺ 3.8 – 5.0 mEq/L) and the PD response pattern as well as the number of subjects requiring dose titration. Based on this review, the DSMC will provide a recommendation to evaluate another starting dose in the age group or to evaluate the current starting dose in additional subjects in the age group. Details regarding DSMC review criteria will be described in a charter and are summarized in the DSMC section of the protocol (Section 8.6).
 
The initial number of subjects for each starting dose level will be three, and up to three starting doses per age group can be evaluated. Subject screening will pause periodically throughout the study to allow for preparation of data and DSMC review and provision of recommendations. Any subjects who are in the Screening Period when the pause is announced may be enrolled provided they meet all eligibility criteria. When the Study Management Committee (SMC; see Section 8.5) and DSMC agree upon the recommended patiromer starting dose for a particular age group based upon safety and PD data review, nine additional subjects (or fewer if more than three subjects were initially enrolled) will be added in that age group to receive the recommended patiromer starting dose. Subjects will not be enrolled into higher starting dose levels once the recommended patiromer starting dose is determined for a particular age group. This will yield a total of 12 subjects per age group at the recommended starting dose and a maximum of 18 subjects per age group.
 
Based on findings from the 12 – < 18 years of age cohort, the DSMC will provide a recommendation to initiate dosing in a younger age group, and provide further guidance regarding the starting doses and titration increments for the younger age groups.
 
In addition, the DSMC will review safety and PD data on an ongoing basis during the Long-Term Treatment Phase for all age groups.

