Once the initial group of subjects at a given starting dose level complete their 14-Day PD / Dose Finding Phase, PD and safety data will be provided to the DSMC. The DSMC will evaluate safety and PD data, as well as the number of subjects requiring dose titration. Based on its review, the DSMC will determine if the starting dose for subjects under review was appropriate, in which case, nine additional subjects (or fewer if more than three subjects were initially enrolled) in the same age group will be enrolled at the same starting dose. If the DSMC determines that the starting dose did not result in an acceptable PD response, and the safety is acceptable, the DSMC will provide a recommendation to evaluate the next starting dose in the age group (see Section 8.6 for detailed information on the DSMC).

Subject screening will pause periodically throughout the study to allow for preparation of data and DSMC review and provision of recommendations. Any subjects who are in the Screening Period when the pause is announced may be enrolled provided they meet all eligibility criteria.

Patiromer dose titration is allowed per a protocol-specified algorithm (See Section 5.2.1). The titrated increment or decrement is planned to be the lowest starting dose for each age group.

All patients treated in the PD / Dose Finding Phase will be included in the Long-Term Treatment Phase.

3.2.3 Long-Term Treatment Phase:

After completion of the 14-Day PD / Dose Finding Phase, subjects then enter a Long-Term Treatment Phase that consists of eight visits over a period of 5.5 months. Study visits consist of Week 3, Week 5, Week 7, Week 10, Week 14, Week 18, Week 22 and Week 26 (see Appendix B). Dose adjustments in the Long-Term Treatment Phase may be made at each study visit starting with the Week 2 (Day 14) Visit according to the titration algorithm (see Section 5.2.1).

At each study visit in the Long-Term Treatment Phase, potassium levels will be measured locally and by central laboratory. ECG evaluations will be performed as soon as possible whenever the local K⁺ level is > 6.0 mEq/L; at the Week 26 (or ET) Visit, an ECG will be performed regardless of potassium level. Additional laboratory assays and assessments will be performed according to the Schedule of Events (see Appendix B). A full list of central laboratory assays is provided in Appendix C.

Study visits at Week 3, Week 10 and Week 22 are optional and may be omitted under the following circumstances:

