8.6 Data and Safety Monitoring Committee

Prior to initiation of the study, an independent DSMC will be established. The DSMC will act in an advisory capacity to Relypsa to monitor the safety of patiromer in subjects who participate in the study. In general, the DSMC responsibilities will include:

- Protect the safety of the study participants in accordance with the study protocol and DSMC Charter
- Review and evaluate all relevant information that may have an impact on the safety of the study participants or the ethics of the study
- Assess risks and benefits to study participants
- Make recommendations to Relypsa concerning continuation, termination or other modifications of the study
- Review safety, dosing and pharmacodynamic data throughout the study

Based on this review, the DSMC will provide a recommendation to evaluate another starting dose in an age group or to evaluate the current dose in additional subjects in that age group. Dose escalation and/or stopping criteria are pre-identified based on pre-specified safety criteria or on the lack of sufficient response as described below.

The DSMC charter will provide additional details concerning the review and recommendation process.

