8.6.1 Dose Escalation

Evaluation of Starting Dose Levels:

During the 14-day PD / Dose Finding Phase the Investigator will be allowed to up-titrate the patiromer dose according to a protocol-specified algorithm. A description of the patiromer dose titration algorithm is provided in Section 5.2.1.

After three subjects complete their 14-Day PD / Dose Finding Phase, PD, dosing and safety data will be provided to the DSMC. The DSMC will evaluate these data, as well as the number of subjects requiring dose titration. Based on its review, the DSMC will determine if the starting dose for subjects under review was acceptable for a recommended starting dose, in which case nine additional subjects (or fewer if more than three subjects were initially enrolled) in the same age group will be enrolled at the same starting dose. If the DSMC determines that the starting dose and/or titration pattern did not result in an acceptable PD response, but the safety was acceptable, the DSMC will provide a recommendation to evaluate the next higher starting dose in the age group.

Subject screening will pause periodically throughout the study to allow for preparation of data and DSMC review and provision of recommendations. Any subjects who are in the Screening Period when the pause is announced may be enrolled provided they meet all eligibility criteria. Details regarding DSMC review criteria are described in the DSMC charter.

The DSMC will evaluate the following subject-level parameters in assessing a patiromer starting dose level:

- Achieving a target serum potassium range of 3.8 – 5.0 mEq/L
- Clinically relevant decrease in serum potassium
- Number of dose up-titrations above the starting dose
- Patient safety information

The DSMC will consider the baseline and change in serum potassium level in determining if an observed decrease in serum potassium is clinically relevant for subjects that do not achieve the target potassium range. In addition, the DSMC will consider the proportion of subjects that had up-titrations of patiromer to ensure a recommended starting dose is close to the effective dose (e.g., up-titrations required in all three subjects may suggest the starting dose was too low).

Section 5.2 describes the planned starting doses in all age groups. The DSMC will recommend the starting doses for the 6 – <12 year old age group upon evaluation of PD and safety data for the

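### Section 1.4 moves a starting dose that is not agreed appropriate to the next higher level with no safety condition, whereas 3.2.2 and 8.6.1 attach acceptable safety to that step

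*Protocol*

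**What the plan says.** Four parts of the protocol describe what happens after the three-subject review.

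- **Section 1.4** makes the review a joint one that covers safety: "The SMC and DSMC will review safety and PD data from the three initial subjects". If both committees find the dose appropriate, the cohort is expanded to 12. Otherwise: "If the SMC and DSMC do not agree that the initial patiromer starting dose evaluated is appropriate, then the next higher patiromer starting dose level" is evaluated in three more subjects.
- **Section 3.2.2** ties the step to two findings on the level under review: "did not result in an acceptable PD response, and the safety is acceptable, the DSMC will provide a recommendation to evaluate the next starting dose".
- **Section 8.6.1**, titled Dose Escalation, does the same for the move to a higher level: "did not result in an acceptable PD response, but the safety was acceptable, the DSMC will provide a recommendation to evaluate the next higher".
- **The synopsis** (DSMC Review / Starting Dose Level Assessment) says only that "the DSMC will provide a recommendation to evaluate another starting dose in the age group" or to continue with the current one. It gives neither a direction nor a safety condition.

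The deciding body differs too. Section 1.4, and the synopsis sentence on adding nine subjects, require the SMC and DSMC to agree. Another synopsis sentence reads "The DSMC will determine a recommended starting dose for each age group", and 3.2.2, 8.6.1 and 9.3 also name the DSMC alone. Under 8.5 the SMC consists of sponsor representatives and the lead investigator.

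**The concern.** The review in 1.4 covers safety as well as response, so a dose can be found not appropriate for either reason. Section 1.4 does not separate the two and gives both the same consequence, a higher dose. Sections 3.2.2 and 8.6.1 do separate them.

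An ethics committee, a DSMC member or a site reading 1.4 would therefore take away a different escalation rule from one reading 8.6.1. The difference falls on the case that matters most for the children enrolled next. By the protocol's own account (1.3) this is the first study of patiromer in this age range, and the recommended starting dose is one of its main products. The documents should state one rule for reaching that dose and say who applies it.

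**Working it through.** **1. The plan's own figures.** These are reproduced first; the point does not depend on them.

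- Minimum N: 3 age groups × (3 + 9) = 36.
- Maximum N: 3 × (3 × 3 + 9) = 54.
- Exact two-sided 95% lower limit for 12 of 12: 0.025^(1/12) = 0.7354, which the plan gives as 73% (truncated).

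All three agree with Protocol 9.3 and SAP 2.3. Adding a safety condition to 1.4, or otherwise aligning the wording, changes none of them.

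**2. The three rules set against each possible finding.**

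| Finding after three subjects | 1.4 | 3.2.2 | 8.6.1 |
|---|---|---|---|
| Dose judged appropriate | Expand to 12 | Expand | Expand |
| Response inadequate, safety acceptable | Next higher dose | Next dose | Next higher dose |
| Dose judged not appropriate on safety | Next higher dose | Condition not met; no action stated | Condition not met; no action stated |

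The sections differ only in the third row.

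**3. Does other text settle the third row?**

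- *Precedence.* The only precedence clause (Protocol 9, repeated in SAP 1) puts the SAP above the protocol. The SAP repeats the sample-size text and gives no escalation rule. Nothing ranks 1.4 below 8.6.1.
- *Stopping criteria (8.6.2).* There are three triggers. Two are DSMC consultations: two subjects with the same severe related GI event, or two with medically similar related unexpected SAEs. The third is one confirmed related unexpected SAE, which bars new starts on, and up-titration to, the level where it occurred; its wording does not mention higher levels. Low magnesium and low potassium are reviewed but are not triggers. A dose rejected on safety short of these triggers is left to the text in step 2.
- *Lower levels.* Each cohort begins at the lowest level in Table 1, so the table holds no lower level after a first rejection.

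**4. Size of the step.** From Table 1, 8.4/4.2 = 16.8/8.4 = 2; 4/2 = 8/4 = 2; 2/1 = 4/2 = 2. Every move to the next level doubles the starting dose for three children. There are two such moves in each of three cohorts, so at most 3 × 2 × 3 = 18 children enter through escalation, which is 54 − 36. This is a ceiling on all escalation, not an estimate of how many would follow a safety rejection.

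**5. How often three children might raise a safety question.** The documents give no rate, so this is an assumption. With a per-child probability p of a safety event, the chance of at least one in three is 1 − (1 − p)³: 14% at p = 0.05, 27% at 0.10, 49% at 0.20 and 66% at 0.30. Not every such event would lead to rejection of the dose. The range shows only that the third row is not a remote case.

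**The case against.** The strongest reply is that 1.4 is a rationale section and the omission is probably one of drafting. The synopsis and 3.2.2 both refer readers to 8.6 for detail. Section 8.6 says: "Dose escalation and/or stopping criteria are pre-identified based on pre-specified safety criteria or on the lack of sufficient response as described below", which points to 8.6.1 and 8.6.2. It also lets the DSMC recommend termination or other modification of the study. Section 1.5 describes one of the doses guiding the selection as below the adult efficacy range, so the expected reason for rejecting a first dose is weak response, where all sections agree. Review criteria and SMC authority are assigned to the DSMC charter and SMC Plan, which are not among the documents. All of this stands, and it lowers the chance that anyone would act on 1.4 against 8.6.1. It does not remove the conflict in the approved text.

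Three stronger readings may tempt a reader, and the documents do not support them.

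- *That the sections order opposite actions.* They do not. For a dose rejected on safety, 3.2.2 and 8.6.1 leave their condition unmet and state no contrary action. They also say that escalation follows if the conditions hold; that it follows only then is an inference from the lack of any other route.
- *That the sponsor's committee could force escalation by withholding agreement.* This strains 1.4, which reads more naturally as a joint judgement that the dose is not right. In 3.2.2 and 8.6.1 the next dose follows a DSMC recommendation. What happens when the committees differ may be set out in the charter or SMC Plan.
- *That the 8.6.1 review list ignores excessive potassium lowering.* The list includes reaching 3.8 – 5.0 mEq/L, which a value below 3.8 fails, and patient safety information. Section 8.6.2 also has the DSMC review low potassium and magnesium.

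**Conclusion.** The point holds as an internal inconsistency in current protocol text. For a starting dose judged not appropriate on safety, 1.4 as written leads to the next higher level, while the escalation condition in 3.2.2 and 8.6.1 is not met. Section 8.6.2 closes this gap only for its defined triggers. The deciding body is stated in two ways.

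If the 1.4 wording were followed in that case, three further children would start at twice the rejected dose. How likely that is cannot be judged from the documents. The conclusion assumes that not appropriate in 1.4 can rest on safety, which follows from the safety data being part of that review, and that the unseen charter and SMC Plan do not override the protocol's wording. The sample size, the precision statement and the analyses are unaffected. The plan should correct this, but it does not undermine the trial's estimates.

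**What to change.** The sponsor and DSMC should reconcile the synopsis (DSMC Review / Starting Dose Level Assessment), 1.4, 3.2.2 and 8.6.1 so that:

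- one escalation rule is written out in one place, with the other sections cross-referring to it;
- the rule is consistent with the stopping criteria in 8.6.2;
- the deciding body is named in the same way throughout, including 9.3 and SAP 2.3, which repeats the 9.3 text;
- the outcome for a dose rejected on safety is stated.

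Which rule is right, and what should follow a safety rejection, is for the sponsor and DSMC; this point takes no position on it. If the charter or SMC Plan already settles any of these items, the protocol can cite it.

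The cost is amended wording, with no added subjects, visits or data. N stays at 36 to 54 and the 73% bound is unchanged.
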